Cover Page

Statistical Analysis Plan

Study Title: Longitudinal Follow-up of Brief Parenting Interventions to Reduce Risk of Child Physical Maltreatment

Identifier: NCT04059185

Document date: 04/18/2024

Statistical Analysis Plan

The power analysis was based on the continuous primary outcome scores at 3-month follow-up. Assuming a significance level of 0.05 in two-tailed tests for the interaction between treatment group and visit type (baseline and follow-up), we would have at least 90% power to detect a standardized effect size of 0.33, if we enrolled 300 participants per group. Conservatively we allowed for a modest amount of autocorrelation of 0.30.

The reported results will follow an Intent to Treat analysis. For the baseline to 3 month follow up analysis, we will fit linear mixed effect models for each of the scale outcomes: Attitudes towards Spanking Scale (ATS), Positive Parenting Practices scale (PPP) and Child Emotional Maladjustment (CEM). The predictors in the models will be group membership (TP2, PN, and Control), visit type (baseline and follow-up) and their interaction along with random intercepts for subjects. We will also report contrasts among treatment groups and visit type based on post-hoc least squares means analyses, using a Benjamini and Hochberg correction to adjust for false discovery rate for multiple comparisons. As a robustness check, we will use difference scores as the outcomes in linear regression model. We will use Full Information Maximum Likelihood to address missingness. Generalized Estimating Equations with a multinomial outcome will be used for the categorical outcome. We will use multiple imputation to maximize use of all available data.

For the 4 year follow up (4Y) analysis, we will fit linear mixed effect models for each of the scale outcomes: ATS, PPP (total and 4 subscales) and CEM (total and 2 subscales). The predictors in the models will be group membership (TP2, PN, and Control), visit type (baseline, 3M, 4Y), and their interaction. Models will also include random intercepts for participants. Generalized estimating equations (GEE's) will be used for the nominal multinomial outcome of spanking behavior, accounting for within-person correlation across timepoints.

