Multiple imputation using chained equations will be used to address missingness and unusually delayed 4Y visits due to the COVID-19 pandemic (number of imputations = 100). Specifically, a new column will be created for “4-year-follow-up” responses on all primary outcomes and filled in with the participant’s true response if they were visited within 5.1 years of their baseline visit (i.e. if their follow-up time was below the third quartile for the sample follow-up time); Otherwise, this value will be set as “missing” and therefore imputed using the multiple imputation procedure. The imputation model will include participants’ actual long-term response values and their observed time lag to long-term visit from baseline interview date, in addition to the primary measures used in the study at all time points, demographic information, and intervention group.

For the RSA outcome measures, linear mixed effects models will be employed to model the effect of the intervention condition on task specific RSA withdrawals. For these questions, children and parent data will be analyzed separately, and the specified model will be identical for both populations. The model will include mean RSA as the dependent variable. Predictors will include Epoch (baseline, social interaction task, or challenge task), Intervention Group, and the interaction of these terms. Random intercepts for participant ID will account for repeated measures across epochs.

After fitting the model, hypotheses will be tested with a series of planned contrasts. Specifically, we will evaluate the statistical significance of the following contrasts:

- TP vs. Control at Baseline, Social Interaction, and Challenge (Hypothesis a; 3 tests)
- PN vs. Control at Baseline, Social Interaction, and Challenge (Hypothesis b; 3 tests)
- Effect of Social Interaction epoch with reference to Baseline for TP vs Control (Hypothesis c, 1 test)
- Effect of Social interaction epoch with reference to Baseline for PN vs. Control (Hypothesis d, 1 test)

- Effect of Challenge task epoch with reference to Baseline for TP vs Control (Hypothesis e, 1 test)
- Effect of Challenge task epoch with reference to Baseline for PN vs. Control (Hypothesis f, 1 test)

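### The 4-year imputation model contains the very response it is meant to replace, so visits after 5.1 years come back essentially unchanged and the delay adjustment does not happen

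*SAP*

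**What the plan says.** The SAP's paragraph on the 4-year imputation states that chained equations with 100 imputations "will be used to address missingness and unusually delayed 4Y visits due to the COVID-19 pandemic". A new 4-year column is made for every primary outcome. It takes the participant's "true response if they were visited within 5.1 years of their baseline visit", which the SAP glosses as "if their follow-up time was below the third quartile for the sample follow-up time". All other values in the column are set to missing and imputed. The imputation model then includes participants' "actual long-term response values and their observed time lag to long-term visit from baseline interview date". The other listed predictors are the primary measures at every time point, demographics and group.

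The 4-year mixed models use group, "visit type (baseline, 3M, 4Y), and their interaction", with random intercepts. They have no term for lag. The same paragraph lists PPP and CEM as totals together with their subscales.

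In the protocol (section 3, Long Term Follow-Up Visit), when clinic activities are postponed after a phone survey, only the pandemic part of that survey is repeated.

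**The concern.** The purpose of blanking late responses is to replace them with what the participant would have given at about four years. That requires a model that learns how the on-time response relates to other information. Here the model is also given the response itself, which equals the target in every row used to fit it. It learns only to copy, and it copies the late values too.

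The 4-year contrast on the primary outcomes answers the sustained-effect question (Protocol section 1, aim 2). Readers would be told that delayed visits had been adjusted for when they had not. If effects fade with time, or if the software lets the two columns impute each other, the contrast itself would also be wrong.

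**Working it through.** **The plan's own figure.** The SAP gives no figure for how the imputation behaves. Its one calculation is 3-month power: effect 0.33, autocorrelation 0.30, 300 per group. The SD of change is √(2 × (1 − 0.30)) = 1.183, the SE is 1.183 × √(2/300) = 0.0966, and 0.33/0.0966 = 3.42. Power is Φ(3.42 − 1.96) = 92.7%, consistent with the stated minimum of 90%. The main result below does not depend on it.

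**The identity.** Let L be the actual long-term response and T the 4-year column. The model for T is fitted only where T is observed, and there T = L. The fit is T = 0 + 1·L + 0·lag + 0·(everything else), with residual variance 0. A draw for a late visit is therefore L. An L-by-lag term would also get coefficient 0. No planned data pair an on-time with a late response from one participant, so nothing could inform the lag effect within persons.

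**Late visits, |imputed − L|, simulated.**
- Normal regression (ridge 1e-5): 0.00001 SD.
- Predictive mean matching (5 donors): mean 0.018, median 0.009 SD. A separate run had single differences of 0.5 to 0.8 SD for extreme values without near donors.

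**Inputs for the contrast (illustration only).**
- From the documents: 400 per arm = 1200/3 (Protocol section 1, Study Design); 75% seen at 3 months (Protocol section 3, 3-Month Follow-Up Visit); 0.33 and 0.30 borrowed from the 3-month power statement.
- Assumed: 75%, 60% or 40% seen long term; normal lags with third quartile 5.1 years and SD 0.7; all fading and drift.
- Settings: 300 trials each, 10 imputations, Monte Carlo error at most 0.006.

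**(1) One-way prediction: L predicts T but not the reverse.** If late visits keep a fraction f of the effect, the expected contrast is 0.33 × (0.75 + 0.25f). At 60% seen:

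| f | formula | as written | no delay adjustment | L and lag removed |
|---|---|---|---|---|
| 100% | 0.330 | 0.327 | 0.328 | 0.332 |
| 50% | 0.289 | 0.289 | 0.288 | 0.324 |
| 0% | 0.248 | 0.249 | 0.243 | 0.327 |

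The scheme as written matches making no adjustment at all.

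**(2) L and T impute each other.** For never-seen participants both are blank, and each reproduces the other's starting value. If those values carry no group difference, the contrast is about 0.33 × share seen. There is no fading in this table:

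| seen | formula | T first | L first | one-way |
|---|---|---|---|---|
| 75% | 0.248 | 0.249 | 0.285 | 0.326 |
| 60% | 0.198 | 0.197 | 0.254 | 0.327 |
| 40% | 0.132 | 0.127 | 0.230 | 0.333 |

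**(3) Software drops L but keeps lag.** The contrast is unbiased in simulation, but late values are predicted at their late lag.

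**Within-arm levels under a common drift of 0.30 SD per year.** Mean lag is 5.1 − 0.6745 × 0.7 = 4.63 years overall, 4.63 + 0.7 × 0.3178/0.25 = 5.52 for late visits and 4.63 − 0.7 × 0.3178/0.75 = 4.33 for on-time visits. The late control mean is then 0.30 × 1.52 = 0.46 SD from the 4-year mean (simulated: 0.45 as written, 0.45 with only L dropped, 0.10 with L and lag both removed). The contrast as written is 0.320, with no bias beyond simulation error.

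**Totals and subscales.** Scoring is not stated. If totals are sums or means of subscales and both enter the imputation, they lock in the same way. In simulation with L and lag removed, the PPP-type total contrast is 0.194 / 0.148 / 0.096 at 75% / 60% / 40% seen, close to 0.33 × 0.75 × share seen = 0.186 / 0.149 / 0.099. With subscales imputed and the total derived it is 0.332 / 0.322 / 0.326.

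**The case against.** The strongest reply is that the sustained-effect question is a comparison with controls, and the contrast may be sound. This stands: under one-way prediction without fading it is 0.327, and 0.320 under common drift. Bias needs either fading, for which the documents give no figure, or mutual prediction, which the SAP neither states nor excludes.

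The drift figure of 0.45 SD concerns late visitors only. For all seen participants in an arm, the deviation from year 4 is 0.30 × 0.63 = 0.19 SD as written and 0.30 × 0.33 = 0.10 SD with L and lag removed, a gap of 0.09 SD. That is the fairer measure of the effect on a reported mean.

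Software might drop the collinear copy. Late values would then not come back unchanged, but the model run would not be the model written, and late values would still be predicted at their late lag.

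Only continuous outcomes were simulated. For nominal spanking behavior the same identity implies perfect prediction, which is argued rather than tested.

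The subscale point is conditional on scoring and on what enters the imputation. It concerns the 4-year analysis; full-information maximum likelihood is specified for the 3-month one.

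Finally, using every observed response is a defensible intent-to-treat analysis and fits the SAP's wish to use all available data. That is a reason to report it, but not to describe it as adjusted for delay.

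**Conclusion.** The concern holds. For regression-type imputation that keeps the listed predictors, the step meant to handle delayed visits leaves about 25% of long-term responses essentially as they were. This follows from the SAP's definition and rests on no assumed input. Nothing in the analysis model or the protocol repairs it.

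Whether the 4-year contrast is biased depends on details the SAP does not give. Under one-way prediction there is no bias without fading, and any late fading passes through in full (0.289 or 0.249 against 0.33 when half or none of the effect remains). Under mutual prediction the contrast shrinks toward zero, to between 0.127 and 0.285 over the assumed shares seen. RSA and CIB outcomes have their own models and are not affected. This should be fixed.

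**What to change.** Do not let the actual long-term response and its 4-year copy appear in the same imputation model.

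**(a) Recommended.** Keep the 5.1-year rule and write:

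> The imputation model for the 4-year columns will include the primary measures at baseline, 3 months and, where available, 1 year, the 4-year columns of the other primary outcomes, demographics and group. Actual long-term responses and their lag will not be included. Where a total is computed from subscales, a total and its own subscales will not be imputed from each other at any time point; subscales will be imputed and the total derived.

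State whether the incomplete 1-year columns are imputed in the same chain or left out. State that late values are assumed missing at random given these variables. Report an analysis using every observed long-term response as a sensitivity analysis. At 60% seen and late effects of 50% / 0%, this wording gave 0.321 / 0.330.

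Cost: late responses go unused in the main analysis, so variance rises by about 1/0.75 = 1.33 (simulated SE about 0.105 against 0.090 at 60% seen). The level estimated is that of on-time visits, averaging 4.3 years under the assumed lags.

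**(b) Alternative.** Keep one long-term column with all observed responses. Put lag and group-by-lag, with a stated functional form, in both the imputation and analysis models, and estimate the contrast at a lag of 4 years.

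Cost: a lag for never-seen participants must be specified, and precision falls. The variance ratio 1 + ((mean lag − 4)/SD)² is 1.18 / 1.80 / 3.33 for lag SD 1.0 / 0.7 / 0.5. Simulated SEs at 60% seen are 0.095 / 0.121 / 0.160, against 0.088 to 0.090 without lag.

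Either option needs only SAP wording and a re-run of the imputation.

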This is a community-based randomized controlled trial. Parents (n=1200) with children 2 to 7 years of age will be recruited from local WIC clinics and by open recruitment. Once consented, they will be enrolled, a baseline interview will be conducted, and they will be randomly assigned to one of 3 conditions: (1) *Triple P-Level 2 only (L2)* intervention, (2) *Play Nicely* intervention, or (3) a “usual care” control group. Three months later, a follow-up interview will be conducted in order to test for intervention effects. 1 year later, a follow-up interview will be conducted. Due to funding restraints, all participants may not receive a 1 year follow-up. In addition, a long term follow-up will be conducted to test sustained effects of the intervention. Participants’ children (n=1200) will be enrolled for the long term follow-up. Children will be invited to participate in order for the adult participant to be observed interacting with the child in several very benign behavioral activities. Adult participants that do not want to enroll their child may participate in the long term follow-up survey which they will have previously consented to. These low-resource intensive parenting interventions are expected to shift parenting attitudes, self-efficacy, and behaviors linked with child physical abuse risk. Even small reductions in such risk across large selected or universal target populations can result in large benefits to the whole population (i.e., Prevention Paradox ¹⁵). Lowered rates of problematic parenting practices will lead to improved child development and behavior. Further, by contributing to a reduction in cumulative adverse childhood experiences, these interventions also are expected to contribute to a long-term reduction in health disparities and risk for major public health problems such as smoking, obesity, drug abuse, risky sexual behavior, mental health disorders, and heart disease among others ^{3,4,16-23}.

Our study name for presentation in the local community is “Tulane Innovations in Positive Parenting Study” (TIPPS).

2. Subject Population

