Baseline Interview: A TIPPS Team Member will then conduct the Baseline interview. Participant responses will be entered by the interviewer into the computer and saved on a secure server via REDCAP. (If WiFi is not available for any reason, the interviewer will provide a paper copy of the survey to the participant and will administer the questionnaire using the paper copy. The paper copy will be kept secure and confidential until the responses can be entered and saved on REDCap.) Response Cards may be provided so that participants can see as well as hear the response options. Whenever possible, our staff will offer childcare in order to minimize distractions. Water and snacks (e.g., pretzels, goldfish) may be offered to participants or their children when available. A series of sensitive questions (Maternal Adverse Childhood Experiences; Hits, Insults, Threatens and Screams; Alcohol Use) will be answered by the participant privately on a paper copy of the survey in order to maximize participant confidentiality and reduce social desirability bias. If an individual indicates suicidal ideation, either by answering affirmatively (i.e. 1=A little bit, 2=Moderately, 3=Quite a bit, 4=Extremely) to "Thoughts of ending your life" in the Brief Symptom Inventory or by mentioning experiencing suicidal feelings or contemplating suicide at any other time during the interview, the Staff Member will follow the Suicide Risk Protocol to connect the participant with the appropriate type of resources.

Once the Baseline Interview is complete (approximately 45 minutes), the participant will be informed of their random assignment to one of three conditions: (1) Triple P-Level 2, (2) Play Nicely, or (3) Control. The next procedure will then depend upon which of the three groups the person is assigned to as follows:

Intervention Procedures:

(1) Triple P-Level 2: The Triple P Specialist will conduct this intervention. This intervention will take

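### The stated missing-data models do not name the baseline distress, adversity, HITS and alcohol measures; adding them is a cheap guard against bias if loss differs by arm or the effect varies with family risk

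*SAP*

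**What the plan says.** The Protocol (section 3, Baseline Interview) collects the relevant risk measures before intervention: "A series of sensitive questions (Maternal Adverse Childhood Experiences; Hits, Insults, Threatens and Screams; Alcohol Use) will be answered by the participant privately". The same interview includes the Brief Symptom Inventory.

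For the 3-month scale outcomes, the SAP fits linear mixed models with group, visit, their interaction and a subject random intercept, and states: "We will use Full Information Maximum Likelihood to address missingness". No auxiliary variable is named. The same paragraph then assigns GEE to the categorical outcome and promises multiple imputation. It does not list the imputation variables or say clearly which outcomes the imputation serves.

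For the 4-year analysis, the SAP gives a list. The chained-equation model contains the actual long-term responses, the time lag to the long-term visit, "in addition to the primary measures used in the study at all time points, demographic information, and intervention group". It does not define the primary measures, but the outcomes it names are ATS, PPP, CEM and spanking behaviour. The four risk measures do not appear.

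The Protocol (section 3, 3-Month Follow-Up Visit) expects at least 25% loss at 3 months, leaving 900 of 1200. Neither document gives a 4-year loss rate, loss by arm, or loss by family risk. Neither plans a sensitivity analysis for data missing not at random.

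**The concern.** Maternal distress, childhood adversity, partner aggression and alcohol use could plausibly predict both non-return and harsh parenting. A missing-data model is valid only if loss is unrelated to the unseen outcome once the variables in that model are taken into account. As written, the 3-month scale models condition on arm and the baseline score of the same scale. The 4-year imputation conditions on more, but not on these measures.

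Two conditions would carry the omission into the arm contrasts: loss whose rate or dependence on risk differs by arm, or an intervention effect that varies with risk. The design makes the first plausible without showing it. Triple P participants have up to an hour with a specialist and a scheduled telephone consult within two weeks, while controls receive a pamphlet (Protocol section 3, Intervention Procedures). Entry to the long-term visit also depends on a screening question about continuing contact with the index child, which is asked after randomisation. On the second, Aim 3 expects effectiveness to vary with perceived norms, so a uniform effect is not the trial's own premise. That aim says nothing about these four measures.

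**Working it through.** **1. The plan's own figures.** The SAP's inputs are: "Assuming a significance level of 0.05 in two-tailed tests for the interaction between treatment group and visit type"; effect 0.33; 300 per group; autocorrelation 0.30. Read as a pairwise difference in change scores:

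- SD of change = √(2 × (1 − 0.30)) = 1.183.
- Standard error of the contrast = 1.183 × √(2/300) = 0.0966.
- 0.33 / 0.0966 = 3.416, and Φ(3.416 − 1.96) = 0.927.

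This agrees with the stated "we would have at least 90% power to detect a standardized effect size of 0.33". Retention also agrees: 1200 × 0.75 = 900, or 300 per group. The point does not depend on the power statement; 0.33 serves only as a yardstick.

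**2. When the omission matters.** A large-sample simulation (1,000,000 per arm, true effect 0.33, higher score worse) made loss depend on a baseline risk score. Follow-up was estimated given the baseline outcome only (the analogue of the 3-month FIML model), then given baseline outcome plus risk score, fitted within arm. Assumed inputs, none in the documents except the 0.30 autocorrelation and the 25% loss:

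- risk–outcome correlation 0.2 to 0.5
- risk–baseline-score correlation 0.3
- baseline–follow-up correlation 0.30
- log-odds of loss 0.7 per SD of risk, where loss depends on risk
- overall loss 25% or 50%

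| Loss pattern | Contrast bias (SD), 25% loss | Contrast bias (SD), 50% loss |
|---|---|---|
| Same rate and same risk dependence in both arms, uniform effect | about 0.00 | about 0.00 |
| Same risk dependence, rates differ (20% v 30%; 45% v 55%) | 0.01–0.03 | 0.01–0.03 |
| Loss depends on risk in one arm only | 0.02–0.07 | 0.03–0.13 |
| Same loss pattern, effect varies by 0.15 SD per SD of risk | about 0.02 | 0.04–0.05 |

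In the first row each arm mean is shifted, by 0.02 to 0.07 at 25% loss and 0.03 to 0.13 at 50%, but the shifts cancel in the contrast. With the risk score included, bias is about 0.00 in every row. Direction depends on who is lost: if higher-risk women leave the intervention arm in particular, the intervention looks better than it is.

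**3. A closed-form cross-check.** Suppose that, given baseline score, women lost from one arm are 0.5 SD higher on risk than women lost from control, with loss fraction p in each arm. Randomisation equalises mean risk across whole arms, so the women retained in that arm must be lower than retained controls by 0.5 × p/(1 − p). The contrast bias is

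bias = b × 0.5 × p/(1 − p), with b = (r − 0.3q)/(1 − 0.3²),

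where r is the risk–outcome correlation, q the baseline–follow-up correlation and 0.3 the risk–baseline correlation.

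- q = 0.3: b = 0.231 (r = 0.3) and 0.341 (r = 0.4). Bias is 0.04 and 0.06 at p = 0.25; 0.12 and 0.17 at p = 0.50.
- q = 0.6: b = 0.132 and 0.242. Bias is 0.02 and 0.04 at p = 0.25; 0.07 and 0.12 at p = 0.50.

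The result is sensitive to q. The 0.30 in the SAP is a planning value for power, which the SAP describes as conservative.

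**4. Credit for what the 4-year model already holds.** As an illustration, add a 3-month score (correlation 0.5 with baseline and with the 4-year outcome, 0.3 with risk) and one other primary measure (0.3 with risk and with the 4-year outcome, 0.4 with the other two scores). With q = 0.3, b falls from 0.231 to about 0.15 and from 0.341 to about 0.26. At p = 0.50 and the same 0.5 SD gap, bias falls from 0.12 to about 0.07 and from 0.17 to about 0.13. The existing list helps but does not replace the risk measures.

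**5. Range.** Across steps 2 and 3, where either condition holds, bias is roughly 0.01 to 0.07 SD at 25% loss and 0.01 to 0.17 SD at 50%. Against 0.33 this is 0.01/0.33 = 3% to 0.07/0.33 = 21%, and 3% to 0.17/0.33 = 52%.

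**The case against.** The strongest reply is that no bias has been shown. A reader might infer that loss related to family risk must by itself bias the 3-month and 4-year contrasts. The documents do not support that: they report no loss by arm or by risk and no effect modification by these measures, and loss alike in all arms with a uniform effect leaves the contrasts about unbiased. This objection stands, and the point is conditional for that reason.

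Second, the 4-year imputation already conditions on the primary measures at all time points, demographics and arm, and uses the actual late responses of women seen after 5.1 years. This also stands in part, as step 4 shows. Because the primary measures are undefined, complete exclusion of the four risk measures is the likely reading, not a certain one.

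Third, the 3-month text is ambiguous. FIML can carry auxiliary variables and the SAP is silent on them; the multiple imputation there has no variable list. A reader might conclude that the plan wrongly handles scale and categorical outcomes at the same visit by two methods. The wording does not settle that, and the split would not be a fault in itself, since ordinary GEE is not likelihood-based and FIML does not apply to it. For the 3-month imputation the supportable criticism is under-specification.

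What the objections do not remove is that the measures are collected and that the stated models name none of them.

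**Conclusion.** The point holds as a cheap improvement, not as a demonstrated bias. The 4-year imputation list and the 3-month FIML models omit four baseline measures that could plausibly predict both loss and outcome, and the 3-month imputation variables are not stated. The contrasts are exposed only if risk-related loss differs by arm or the effect varies with risk; otherwise the benefit is a little precision.

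The illustrative sizes in step 5 rest on assumed correlations, loss patterns and arm gaps; the 50% loss is also assumed. The upper end, 0.17 SD, needs a 0.5 SD arm gap among the women lost, a baseline–follow-up correlation of only 0.3 and no help from the variables already in the 4-year model. It should not be read as an expected bias.

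**What to change.** - **SAP, 4-year multiple imputation paragraph:** add the baseline Brief Symptom Inventory, maternal adverse childhood experiences, HITS and alcohol use as auxiliary variables. Impute within arm, or include group-by-auxiliary terms, so that an effect varying with risk is not smoothed away. Recruitment route and enrolment date are optional additions.
- **SAP, 3-month paragraph:** use the same auxiliary set for all outcomes, by multiple imputation or, for the scales, by FIML with auxiliary variables. State which outcomes the multiple imputation serves and list its variables. Define the primary measures.
- **Reporting:** tabulate loss by arm and by these four measures at 3 months and 4 years, so readers can judge whether the conditions for bias are present.

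The cost is SAP wording, a longer imputation run and a few more incomplete variables in the chained equations. No new data are needed, and the estimand and analysis models are unchanged.

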- (2) **To establish sustained effects of brief parenting interventions on both parenting behaviors and child outcomes.** Our working hypothesis is that parent and child outcomes will be improved (e.g., reduced parental use of CP and reduced child emotional and behavioral maladjustment) in both intervention conditions compared to controls at long term follow-up. In addition, when compared to controls, children and parents randomized to either intervention will exhibit better physiologic responses when playing or talking together.
- (3) Determine if intervention effectiveness is modified by parents’ perceived norms. Our working hypothesis is that stronger perceived injunctive norms by parents of professionals (e.g.,

pediatricians, mental health, and religious) supportive of physical discipline will be associated with reduced intervention effectiveness.

(4) **To establish the sustained effects of two brief parenting interventions on perceived injunctive norms about CP and support for CP use.** Our working hypothesis is that parents will have and perceive less support for CP use (including amongst professionals trusted for parenting advice) in both intervention conditions compared to the control condition at long-term follow-up.

Study Design

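### Twenty RSA contrasts are tested as hypotheses with no stated sign, level, multiplicity rule or exploratory label, and the SAP's only correction is not extended to the 4-year or CIB analyses

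*SAP*

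**What the plan says.** - **RSA (SAP, RSA analysis).** After the mixed model is fitted, "we will evaluate the statistical significance of the following contrasts". The list has 3 + 3 + 1 + 1 + 1 + 1 = 10 entries under hypotheses a to f. Children and parents are analysed separately, and "the specified model will be identical for both populations". No sign, level, adjustment or exploratory label follows.
- **RSA direction (Protocol section 1, Aim 2).** Children and parents in either intervention "will exhibit better physiologic responses when playing or talking together". The SAP's robustness model defines withdrawal as baseline minus social-interaction RSA, but neither document says which direction is better.
- **Level (SAP, power analysis).** "Assuming a significance level of 0.05 in two-tailed tests for the interaction between treatment group and visit type (baseline and follow-up"). This is the only level in the SAP.
- **Correction (SAP, baseline to 3-month analysis).** Least-squares-means contrasts are reported "using a Benjamini and Hochberg correction to adjust for false discovery rate for multiple comparisons". The 4-year, RSA and CIB text does not repeat this.
- **4-year outcomes (SAP).** Models are named for "ATS, PPP (total and 4 subscales) and CEM (total and 2 subscales"), plus a multinomial model for spanking. No contrasts are listed.
- **CIB (SAP).** Eight sub-constructs, each with a stated direction, and the main attention on each intervention against control. The hypothesis test is described only for the case where the group-by-task interaction is dropped.
- **Ranking.** The scale outcomes are called primary in the power paragraph ("The power analysis was based on the continuous primary outcome scores at 3-month follow-up") and in the 4-year imputation text ("responses on all primary outcomes"). RSA and CIB are not.

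**The concern.** The RSA contrasts are presented as tests of named hypotheses, so a significant result will naturally be read as confirming one. With no sign fixed in advance, a rejection in either direction, in either arm, in mothers or in children, could be reported as support. Four of the 20 contrasts (2 arms × 2 populations) compare arms at the baseline epoch, which Aim 2's wording about playing or talking together does not cover. At stake is a physiological claim that chance alone would supply in about half of such trials. The 4-year outcomes carry the primary label, yet they too have no error rule, and their contrasts are left to be chosen later.

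**Working it through.** **1. The plan's own figure.** The SAP claims at least 90% power for 300 per group, a standardized effect of 0.33, two-tailed 0.05 and autocorrelation 0.30. SD of change = √(2(1 − 0.30)) = 1.183; standard error = 1.183 × √(2/300) = 0.0966; 0.33/0.0966 = 3.42; power = Φ(3.42 − 1.96) = 92.7%. It reproduces, but it concerns the 3-month interaction and says nothing about RSA, CIB or 4 years.

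**2. Counts.** RSA: 10 × 2 populations = 20. CIB: (3 + 3 + 2) × 2 arms = 16. 4-year, assuming each arm is compared with control: (1 + 5 + 3) × 2 = 18, or 20 if spanking is added.

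**3. RSA with no true effect, two-sided 0.05 each.** Expected false positives: 20 × 0.05 = 1.0. Independence would give 1 − 0.95^20 = 64%, but the tests are not independent. Hypotheses c and e are differences of the a contrasts, d and f are differences of the b contrasts, and both arms share one control. I therefore simulated the actual contrasts: equal arms, 200,000 runs, change contrast z = (d_task − d_baseline)/√(2(1 − ρ)), where d is the standardized arm-minus-control difference. The documents give no correlations, so ρ (between epochs) and the mother-child correlation are assumptions.

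| At least one rejection | ρ = 0.5 | ρ = 0.7 | ρ = 0.85 |
|---|---|---|---|
| One population (10 tests) | 31% | 30% | 28% |
| Both (20), mother-child 0 | 52% | 51% | 49% |
| Both (20), mother-child 0.3 | 51% | 50% | 48% |
| One population, one direction only | 17% | 16% | 15% |
| Benjamini-Hochberg, one family of 10 | 4.5% | 4.4% | 4.2% |
| Benjamini-Hochberg, either of two families | 8.8% | 8.7% | 8.2% |

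One direction over both populations: 1 − (1 − 0.17)² = 31% at ρ = 0.5, falling to about 27% at ρ = 0.85 with mother-child correlation 0.3.

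**4. CIB and 4-year, same method, between-outcome correlation 0 to 0.7.**
- Any favourable result: CIB 31% down to 16%; 4-year 34% to 17% (18 tests) or 37% to 18% (20 tests).
- Any result in either direction: CIB 53% to 32%; 4-year, 18 tests, 58% to 34%.

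**5. If both arms had to succeed on the same outcome.** With neither arm effective, the chance is 2.3–3.6% for CIB and 2.5–4.5% at 4 years. If one arm truly works on every outcome (80–90% power each) and the other does nothing, the chance of wrongly declaring both successful on some outcome is 9–18% for CIB and 10–22% for 9 or 10 four-year outcomes.

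**6. What the correction costs for RSA.** Take a change contrast with 80% unadjusted power (mean z = 2.80) and apply Benjamini-Hochberg within the family of ten.
- Effect in one arm and one task (2 of 10 contrasts true): power 52–56%.
- One arm, both tasks (4 true): 57–63%.
- Both arms, both tasks (8 true): 66–72%.

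Across these cases the chance of any false positive is 5–9%, against 9–27% unadjusted.

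**7. CIB pre-test.** With no interaction, chance retains it for at least one of eight outcomes in 20–34% of trials (upper end: 1 − 0.95^8 = 34%). If the retained branch were then read task by task, the per-arm error for one outcome would rise only from 5% to 5.3–6.7%.

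**The case against.** The best reply is that the 0.05 level and Benjamini-Hochberg were meant for the whole SAP and that RSA is plainly secondary. Part of this stands. Nothing in the SAP confines the correction to 3 months in so many words, and the primary label does give a partial ranking. But both rules sit inside 3-month text, no later paragraph takes them up, and the ranking carries no error-control consequence. A reader can only guess at the scope.

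It is also fair that the RSA text is not devoid of context: the model is framed around withdrawal, and withdrawal is defined. Which direction would be better is still unstated.

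Four stronger readings are tempting, and the documents do not support them.
- **That the RSA error is 64%.** This needs independent tests, which the list rules out.
- **That CIB and the 4-year outcomes are at lower risk than RSA.** This compares two-sided RSA figures with one-direction figures for the others. On a like-for-like count the ranges overlap.
- **That predicting benefit in both arms already protects CIB and the 4-year outcomes.** Neither document says that both arms must succeed on the same outcome, and such a rule would not hold 5% if one arm works (step 5).
- **That the CIB pre-test must go.** An inflation to at most 6.7% does not justify that. The gap is one unnamed test.

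**Conclusion.** The point holds. As written, 20 RSA hypothesis tests have no sign, level, multiplicity rule or exploratory label, and at two-sided 0.05 chance alone gives at least one rejection in 28–31% of trials per population and 48–52% overall. The counts and the SAP's silence are certain. The percentages rest on equal arms, a shared control, epoch correlation 0.5–0.85 and mother-child correlation 0–0.3, none of which the documents supply. The 4-year and CIB analyses share the missing error rule, with directions stated, and their risk should not be described as smaller. The undefined CIB branch is minor. This should be corrected in the SAP; it does not touch the 3-month analysis.

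**What to change.** 1. **RSA.** State the level and the sign that counts as support for each contrast, including whether the baseline-epoch contrasts belong to the hypotheses. Then choose one of two options.
   - Apply the SAP's own Benjamini-Hochberg correction within each population's ten contrasts. With no true effect this gives a 4–5% chance of any rejection per family and 8–9% across both. The cost is the power loss in step 6. The method controls the false discovery rate, so the 4–5% figure holds only when nothing is real.
   - Label RSA exploratory and draw no confirmatory conclusion. This costs no power but gives up a confirmatory RSA claim.
2. **4-year and CIB.** State that Benjamini-Hochberg also applies to the 4-year outcomes, which the SAP calls primary, and to CIB, or label them exploratory. List the 4-year contrasts, including the spanking test. The power cost can be large: a single true effect among 16–20 contrasts, with 80% power unadjusted, keeps about 41–45%.
3. **CIB, minor.** Name the arm-versus-control contrast to be tested if the interaction is retained, for example the task-averaged one. That average can mask task-specific effects, which the SAP does not hypothesise. Removing the pre-test is optional.

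All three are changes of SAP wording; no further data are needed.
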